### 5.2 Demographics and Baseline Subject Characteristics

Number of subjects screened will be summarised by treatment group and number and percents of subjects randomised and/or re-screened will be also summarised. Data of subjects included and excluded in FAS, PPS, and Safety Set with the reason of exclusion of any analysis set will be summarised and listed.

Reasons of exclusion from the Safety Set will be presented as follows:

- Not randomised.
- No treatment received.

Reasons of exclusion from the FAS will be presented as follows:

- Not randomised,
- No treatment received,
- No post-baseline assessment.

Subject demographic: sex, age, age in categories for adults: 18-29/30-49/50-65 years, race: American Indian or Alaska Native/Asian/Black or African American/Native Hawaiian or Other Pacific Islander/White/Other/Not Reported/Unknown, ethnicity: Hispanic or Latino/Not Hispanic or Latino/Not Reported/Unknown will be collected on the Demographics CRF page.

Baseline characteristics data at screening or at baseline (see section 5.1.2. for definition of the baseline):

- body weight, body weight in categories (<60, ≥60 kg), body mass index (BMI), BMI in categories for adults: <18.5,18.5-25/25-30/≥30 kg/m² will be collected on the Vital Signs CRF page
- iron parameters (total serum iron, ferritin, transferrin, calculated TSAT) will be collected from Central Lab.
- aetiology of beta-thalassemia (i.e. beta-thal Genotype if available and/or Beta-thal diagnosis)
  and the time to first treatment intake from the date of the diagnosis (in years), blood transfusion
  history (Yes/No) will be collected with time of last transfusion (in months) at treatment start for
  subjects with blood transfusion history on the Aetiology and Clinical Presentation, Transfusion
  CRF page.
- haemoglobin value will be collected via central review assessment.
- prior or ongoing at baseline iron chelation therapy (Anatomical Therapeutic Chemical (ATC) code = V03AC) will be collected in Prior or Concomitant Medication CRF page.
- prior or ongoing at baseline Hydroxyurea therapy (ATC code = L01XX) will be collected in Prior or Concomitant Medication CRF page.
- prior splenectomy (yes, no) subjects with at least one splenectomy recorded will be presented as splenectomy = yes.
- MRI Liver iron content (mg/g dry weight) will be collected from MRI central reading.

The Demographics and baseline Characteristics will be summarized and listed.

### 5.3 Medical History and Concurrent Medical Conditions

Medical history will consist of significant conditions or diseases that stopped at or before Screening. Ongoing conditions will be considered as concurrent medical conditions. Medical history and concurrent medical conditions will be coded using MedDRA [Version 23.0 or higher]. All medical history and associated concurrent medication condition will be listed, and the number and percentage of subjects with any medical history as well as number of events will be summarized by SOC and preferred term for each treatment group.

### 5.4 Prior and Concomitant Medications and Procedures

All medications will be coded using the current version of the World Health Organization Drug (WHO Drug) dictionary [Mar2020 B3G].

Prior medications will be defined as all medications taken before the first dose of study drug with a stop date prior to the first dose of study drug.

Concomitant medications will be defined as all medications with a start date before, on or after the first dose of study drug and with a stop date on or after the first dose of study drug or with a missing stop date.

Prior and concomitant medication will be summarized by number and percentage of subjects. If any prior or concomitant medication is classified into multiple ATC classes, the medication will be summarized separately under each of these ATC classes. The summary tables will be sorted by decreasing frequency of treatment group and decreasing frequency of drug in a given drug class (therapeutic subgroup [2nd level of the ATC classification], chemical subgroup [4th level of the ATC classification] and Preferred Name). In case of equal frequency regarding drug, alphabetical order will be used. A same medication or procedure during the study for one subject will be counted once.

Prior procedures will be defined as all procedures performed before the first dose of study drug with a stop date prior to the first dose of study drug.

Concomitant procedures will be defined as all procedures with a start date before, on or after the first dose of study drug and with a stop date on or after the first dose of study drug or with a missing stop date.

Prior and concomitant procedures will be summarized by displaying the counts and percentages of subjects with at least 1 prior procedures, 1 concomitant procedures and the number of prior and concomitant procedures.

Listings with all prior and concomitant medications and procedures will be provided including the flag for prior, concomitant. Study days will be displayed with start and stop dates.

### 5.5 Study Drug Exposure and Compliance

The total amount of study drug taken will be calculated for each subject from the difference between the amount of drug given and the amount of drug returned. It will be compared to the amount expected to be taken by subject to calculate the percentage compliance to treatment.

Duration of study drug (in days) = Date of last intake of study medication - Start date of treatment +1

Total amount of study drug (number of capsules) = Number of capsules dispensed - Number of capsules returned

Expected amount of study drug (number of capsules) will be defined depending of body weight at screening as follows:

- if body weight at screening < 60 kg, (study day of date of visit Week 12/EOT 1) x 2 +1
- if body weight at screening >= 60 kg, (study day of date of visit Week 12/EOT-1) x 4 +2

Overall compliance (%) = (Total amount of study drug / Expected amount of study drug)\*100.

Morning dose compliance will be calculated and described after study unblinding. Indeed, identification of the kit numbers to the Morning doses or Evening doses will be needed for the calculation.

Total morning amount of study drug (number of capsules) = Number of morning capsules dispensed - Number of morning capsules returned

Expected morning amount of study drug (number of capsules) will be defined depending of body weight at screening as follows:

- if body weight at screening < 60 kg, (study day of date of visit Week 12/EOT-1) +1

- if body weight at screening >= 60 kg, (study day of date of visit week 12/EOT-1) x 2 + 2

Morning compliance (%) = (Total morning amount of study drug / Expected morning amount of study drug)\*100.

The duration of study participation (Date of last assessment – Date of first dose of study drug +1) will be also calculated for each subject and described in summary table. Date of last assessment will be defined as the latest date out of: last contact date, laboratory assessment date, concomitant medication/concomitant procedure/adverse event start date or end date, physical examination date, vital sign assessment date, ECG assessment date, etc..

Study days will be displayed with dispensation, interruption and end dates in listings.

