5.4.2 Withdrawal of Subjects from Study Drug

Study drug must be stopped if there is any clinically relevant AE, laboratory abnormality, inter-current illness or health condition requiring medical treatment, or significant worsening of inter-current illness which, in the opinion of the Investigator, indicates that continued participation in the study is not in the best interest of the subject. The subject concerned will remain under follow-up and the subsequent visits should be performed in accordance with the protocol schedule. Whether the subject should receive additional doses of study treatment will be discussed with the Medical Monitor and will be decided on a case by case basis. If study drug is stopped prematurely for any one subject, the subject concerned will not be replaced.

Subjects may be withdrawn from the study drug if in the opinion of the Medical Monitor or the Investigator there would be a risk to the subject's safety if they received any further dose of study drug.

Study drug must be stopped if any of the below criteria may apply:

- A potentially life-threatening (Grade 4) anaemia according to FDA toxicity grading scale for healthy adult and adolescent volunteers including Hb <8.0 g/dl (5.0 mmol/l) for female subjects or <8.5 g/dl (5.3 mmol/l) for male subjects, and with an absolute Hb drop from baseline >2 g/dl for males and females, and confirmed by subsequent repeat ≥24 hours apart [14].
- Serum transaminases (ALT or AST) >3x ULN range and total bilirubin >2x ULN (confirmed by subsequent repeat \geq 24 hours apart).
- ALT or AST >3x ULN (confirmed by subsequent repeat ≥24 hours apart) with the appearance or worsening of symptoms felt by the Investigator to be potentially related to hepatic inflammation, such as fatigue, nausea, vomiting, right upper quadrant pain or tenderness, fever, rash, or eosinophilia.

- Major protocol deviations, including noncompliance or lost to follow-up.
- Use of a non-permitted concomitant medication.
- Participation in any other clinical study during the duration of this clinical study.
- Loss of ability to freely provide consent through imprisonment or involuntary incarceration for treatment of either a psychiatric or physical (e.g., infectious disease) illness.
- Inability to comply with the protocol or study procedures.

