8.2 End of Treatment (or Early Discontinuation) Procedures

A visit will take place on completion of the treatment or early discontinuation/withdrawal (i.e., at Week 12 (Visit 8)). All assessments should be performed as detailed in Table 1 end of treatment, V8.

Visit window for end of treatment visit is ± 3 days.

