9.1.4 Post-randomisation Visits V4 (Week 1) to V8 (Week 12 or Early Discontinuation)

- Subjects will return to the out-patient clinic at 1 (±1 day), 2 (±2 days), 4 (±3 days), 8 (±3 days) and 12 weeks (±3 days) after randomisation.
- If a subject cannot return to the site for a study visit due to COVID-19 pandemic, the Investigator will conduct a remote visit (e.g., telemedicine, phone call), a visit at the subject's home, or in facilities near to the subject's home to evaluate subject safety and eligibility to continue the study therapy, if applicable and as per local country guidance.
- At the remote/home visits the Investigator should at minimum perform the following: evaluation of the subject's general condition, collection of information on any new and ongoing adverse events, collection of information on the IMP intake and concomitant medications use. Scheduled urine samples may be collected at a home visit, or in laboratories near to the subject's home and should be processed locally. Scheduled blood samples may also be collected at home visit or laboratories near to the subject's home and sent to the central laboratory if possible, otherwise processed locally. Safety analyses such as haematology panel (RBC, Hb, haematocrit, mean corpuscular volume, mean corpuscular Hb, mean corpuscular Hb concentration, white blood cell count with differential, platelets count), coagulation (prothrombin time, activated partial thromboplastin time, thrombin time) and liver function tests (ALT, AST, GGT, total bilirubin, alkaline phosphatase) should be done at the minimum.
- Subjects will have to come in the morning of the visit before taking the study medication, and have to come on an empty stomach. Drinking of water ad libitum is allowed. If a subject is not able to visit the site for IMP resupply due to COVID-19 pandemic, a direct shipment of the study drug to the patient home/place of stay can be implemented, if allowed by the local regulations. The shipment will be performed by a logistics provider in a traceable and temperature-controlled manner.

- During the out-patient visits, the Investigator will check the vital signs (including weight at V8 only), also for AEs, check concomitant medication. On Visit 8 also a physical examination will be done.

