9.1.5 Safety Follow-up Visit V9 (EOS Visit)

• All subjects, whether completing the treatment or who have withdrawn prematurely, will be followed up 4 weeks (28±4 days) after their last administration of study treatment to collect any new AEs and concomitant medications. This visit may be conducted by telephone call or as an in-clinic visit.

•

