### 4.5 Protocol Deviations

The protocol deviations, classified as major by Vifor in the Project Specific Protocol Deviation List version 7.0 dated 26 November 2021 will be identified for all subjects by either site monitoring, medical review processes or programming and confirmed prior to or at the Data Review Meeting at the latest.

Population	Category	Sub category	Description	Vifor's	l
------------	----------	--------------	-------------	---------	---

				classification
PPS	2. Study Conduct/ Procedures	A. Inclusion/ Exclusion Criteria	Failure to complete inclusion criteria #1	Major
PPS	2. Study Conduct/ Procedures	B. Screening	Safety and Haematology     Laboratory samples not taken     at screening and baseline visit     prior to first dosing	Major
PPS	2. Study Conduct/ Procedures	B. Screening	9. Safety and Haematology Laboratory samples: results needed for eligibilty confirmation missing at screening and baseline visit prior to first dosing.	Major
PPS	2. Study Conduct/ Procedures	B. Screening	21. Randomization errors (e.g. incorrect randomization process interaction with IVRS system) resulting in incorrect allocation of the study therapy	Major
PPS	2. Study Conduct/ Procedures	D. Study Restrictions/ Withdrawal Criteria	Non-compliance with protocol restrictions (e.g. use of prohibited medication or prohibited treatment therapy)	Major
PPS	2. Study Conduct/ Procedures	D. Study Restrictions/ Withdrawal Criteria	2. Non-compliance with subject withdrawal criteria defined in the protocol (i.e. subject continued in study but should have been withdrawn).	Major
PPS	2. Study Conduct/ Procedures	E. Dose Formulation/ Dose Administration	2. Incorrect IMP dose intake: Patient took less than 80% of prescribed doses or took more than 105% of prescribed doses. To be assessed during the course of the study (V3 to V8)	Major
PPS	2. Study Conduct/ Procedures	E. Dose Formulation/ Dose Administration	3. Incorrect subject IMP kit given OR wrong dose regimen (total daily dose) assigned based on screening body weigth	Major

All protocol deviations will be presented in the data listings, including the nature of the protocol deviation, non-important or important.

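### SAP 5.5 runs the expected capsule count to the Week 12/EOT visit with no term for a safety-directed stop or interruption, so full adherence to a Day 28 safety stop scores about 33% if the visit schedule is kept.

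*SAP*

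**What the plan says.** SAP 5.5 takes capsules dispensed minus capsules returned as the amount taken, and states the purpose of the ratio: "It will be compared to the amount expected to be taken by subject to calculate the percentage compliance to treatment". The expected amount is then built from two items only, screening weight and one visit day. For subjects of 60 kg or more it is "if body weight at screening >= 60 kg, (study day of date of visit Week 12/EOT-1) x 4 +2". The lighter group has one capsule per intake instead of two, and the two morning-only counts use the same visit day. None of the four expressions refers to last intake, an interruption or a stop. Exposure in the same section does end at the last dose: "Duration of study drug (in days) = Date of last intake of study medication - Start date of treatment +1".

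Protocol 5.4.2 obliges the investigator to stop drug for safety reasons, including confirmed haemoglobin and liver criteria, and also for noncompliance, loss to follow-up or inability to comply. Of a subject taken off drug it says: "The subject concerned will remain under follow-up and the subsequent visits should be performed in accordance with the protocol schedule".

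Other protocol text points to an earlier V8. Section 8.2 says: "A visit will take place on completion of the treatment or early discontinuation/withdrawal". The heading of 9.1.4 likewise treats V8 as the early-discontinuation visit, and 9.1.5 says subjects "will be followed up 4 weeks (28±4 days) after their last administration of study treatment".

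SAP 4.5 lists as a major deviation for the per-protocol set (PPS): "Patient took less than 80% of prescribed doses or took more than 105% of prescribed doses". It is assessed over V3 to V8 and does not cite 5.5.

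**The concern.** The ratio is meant to show whether subjects took what they were told to take. For a completer it does. For a subject whose drug was stopped for safety and who then attends V8 as scheduled, the denominator includes weeks of capsules that nobody prescribed. A stop that the protocol requires is then displayed as poor adherence. The same section would give that subject a 28-day exposure and an expected count running to Day 84.

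The figure also depends on something unrelated to adherence, namely when the site holds V8. Two subjects with identical dosing could be reported at about 33% and about 100%.

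At stake are the readability of the compliance table in a trial whose primary objective is safety and tolerability and, conditionally, who stays in the PPS.

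**Working it through.** **Inputs.** Expected counts, amount taken and compliance ratio: SAP 5.5. Week 12 target Day 84 with a window of ±3 days: protocol Table 1 and 8.2. V9 timing: protocol 9.1.5. The 80% and 105% limits: SAP 4.5. The stop days are illustrations, not document figures. In the lighter-group overall formula the minus sign before the 1 is not visible in the text available here; it is read as minus, as in the other three.

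**Formulas.** Let k be capsules per intake (1 below 60 kg, 2 otherwise), D the study day of V8, and s the stop day with the morning dose as last dose.
- Overall expected = k × [2(D − 1) + 1] = k(2D − 1)
- Overall taken under full adherence = k(2s − 1)
- Morning expected = kD; morning taken = ks

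k cancels, so both weight groups give the same percentage.

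**Completer.** The documents state no compliance figure to reproduce. As a check, D = s = 84 gives 167/167 or 334/334 = 100%, so the formula is right for completers.

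**Safety stop, V8 on Day 84.**

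| Stop day | Overall | Morning |
|---|---|---|
| 28 | 55/167 = 110/334 = 32.9% | 28/84 = 56/168 = 33.3% |
| 56 | 111/167 = 222/334 = 66.5% | 56/84 = 112/168 = 66.7% |
| 67 | 133/167 = 79.6% | 67/84 = 79.8% |
| 68 | 135/167 = 80.8% | 68/84 = 81.0% |

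Full adherence to any stop up to Day 67 scores below 80%. Over the V8 window, the Day 28 figure runs from 55/161 = 34.2% (Day 81) to 55/173 = 31.8% (Day 87). The last stop day scoring below 80% moves to Day 64 (127/161 = 78.9%) or Day 69 (137/173 = 79.2%).

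**Safety stop on Day 28, V8 held as the discontinuation visit.**
- Same day: 55/55 = 100%
- 3 days later (D = 31): 55/61 = 90.2%
- 7 days later (D = 35): 55/69 = 79.7%

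**V9 cross-check.** For a Day 28 last dose, V9 falls on Day 28 + 28 ± 4 = Day 52 to 60, before a V8 on Day 84. The two protocol instructions do not fit together for this subject.

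**Directed interruption with restart.** If w intakes are withheld and all others taken, the Day 84 ratio is (167 − w)/167. It falls below 80% from w = 34 (133/167 = 79.6%), which is 17 days.

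**After the correction.** Ending the count at the Day 28 morning dose gives 55/55 = 110/110 = 100%. If that day's evening dose was prescribed and taken but not counted as expected, the ratio would be 2s/(2s − 1), which exceeds 105% up to Day 10 (20/19 = 105.3%; Day 11: 22/21 = 104.8%). The evening intake therefore has to be counted.

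**The case against.** The strongest reply is that the formula names the Week 12/EOT visit, not Day 84. Protocol 8.2, the 9.1.4 heading and the V9 timing all suit an EOT visit held at discontinuation, and then the figure is 100%. The visit-schedule sentence in 5.4.2 is followed by a case-by-case decision on further dosing, so it may have temporary stops in mind. This stands as far as it goes: the 33% is conditional and cannot be called certain. It does not clear the SAP, because 5.4.2 states the schedule rule without that limit and 5.5 does not choose between the dates. Even with an early V8, a seven-day delay takes full adherence below 80%.

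A second reply is that scoring intake against the planned 84-day course is a legitimate convention, and that the stop is visible elsewhere. Exposure duration, interruption and end dates, and adverse events leading to treatment discontinuation are all reported. The visibility is real and limits the harm. The convention does not match the stated purpose of the ratio, which is the amount the subject was expected to take.

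A third concerns the remedy. Applying it to every 5.4.2 stop would flatter real non-adherence, because that list includes noncompliance. A subject who abandons drug after the Day 20 morning dose and is stopped for noncompliance on Day 28 now scores 39/167 = 23.4% with V8 on Day 84. A blanket rule would raise this to 39/55 = 70.9%, or to 39/39 = 100% if the last intake were used. This objection stands, and the change has to be limited to safety stops.

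A reader might infer that adherent subjects stopped for safety will be dropped from the PPS. The documents do not say so. The SAP 4.5 rule is worded in prescribed doses, does not cite 5.5, and membership is settled at the blind data review. Morning compliance is calculated only after unblinding, so it cannot feed that review.

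**Conclusion.** The point holds in conditional form and is minor. On the path set out in protocol 5.4.2, with V8 near Day 84, the written rule reports full adherence to a Day 28 safety stop as 32.9% overall (31.8% to 34.2% across the visit window) and 33.3% for the morning dose. If V8 is held at discontinuation it reports 100%, less any visit delay. These figures assume a last dose on the morning of Day 28.

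The safety set and full analysis set are unaffected, and all analyses are descriptive. PPS membership changes only if the 5.5 ratio is used for the 80-105% test. The documents do not give the number of such stops; it could be zero, and none is assumed. It would go too far to infer that the compliance table will be wrong whatever happens, or that the safety conclusions are distorted.

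**What to change.** In SAP 5.5, for subjects whose drug is stopped for an adverse event, laboratory or other safety criterion in protocol 5.4.2:
- End all four expected counts (overall and morning, both weight groups) at the last directed dose, taken from the end-of-treatment date. SAP 5.1.4 already has a rule for when that date is missing.
- In the overall counts, include that day's evening intake if it was prescribed.

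For any documented investigator-directed interruption, subtract the doses withheld from the expected count.

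Keep the V8 date for completers, for unprompted stops, and for 5.4.2 stops due to noncompliance, loss to follow-up or inability to comply, so that real non-adherence still shows.

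The cost is a short SAP addition and a small programming change before unblinding. End-of-treatment and interruption dates are already handled or listed under the SAP. The reason for each stop must be classified at the blind data review; the CRF is not among the documents, so it cannot be confirmed that the reason is captured for stops not caused by an adverse event. A further downside is that adherent subjects with short exposure may stay in the PPS.

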# 5.6 **Efficacy Analyses** 5.6.1 Primary Efficacy Analysis Not applicable for this study. 5.6.2 Secondary Efficacy Analysis Not applicable for this study.

	1
	_
_	

[VIT-2763-THAL-201] SAP [Final version V1.0 29-Nov-2021]

	J
 	

